2.15 Section 18.5 Interim Analysis

...

All main conclusions from the trial will be based on this reporting. Furthermore, an interim analysis will be performed when the patients enrolled in the randomised part of the Extension have completed part 1.

In addition interim analyses including data from the extension phase part 2 are planned prior to submission of Biologics License Application and Marketing Authorisation Application.

2.16 Section 25 Retention of Clinical Trial Documentation and Human Biosamples

25.1 Retention of Clinical Trial Documentation

...

Novo Nordisk will maintain Novo Nordisk’s documentation pertaining to the trial as long as the product is on the market plus 20 years. The files from the Investigator site/institution will be retained 15 years after the completion of the trial, or longer if required by national regulations.

25.2 Retention of Human Biosamples

If allowed according to local law leftover blood samples may be retained for later analysis for further characterisation until marketing authorisation approval or until the research project terminates, but no longer than 15 years from end of trial after which they will be destroyed. As new biomarkers related to the disease and/or safety, efficacy, or mechanism of action may evolve the analyses may also include biomarkers that are unknown at present or have not been included in the scientific hypothesis at initiation of the trial. The samples will be stored at a Novo Nordisk designated central laboratory. Samples might be transferred to other countries, if not prohibited by local regulations. The patient’s identity will remain confidential and samples will only be marked and identified by a unique sample ID. No direct identification of the patient will be stored together

with the samples. The analyses will not have any medical consequences for the patients or their relatives.

Only Novo Nordisk staff and central laboratory personnel (if applicable) will have access to the stored blood samples.

In the event that the blood samples are used in the future, the investigator will become directly informed by Novo Nordisk about the results if the findings are deemed clinically and analytically valid and quantifiable. Patients or parent(s)/LAR may at any time contact the investigator if they wish to be informed about results derived from stored blood samples obtained from their own body.

Protocol Amendment
Trial ID: NN7088-3859
UTN: U1111-1119-7416
EudraCT No.: 2011-001142-15

~~CONFIDENTIAL~~

Date:
Version:
Status:
Page:

23 January 2017
1.0
Final
1 of 3

Novo Nordisk

Protocol Amendment
no 20
to Protocol, final version 12.0
dated 02 May 2016

Trial ID: NN7088-3859
pathfinder™ 2

A Multi-national Trial Evaluating Safety and Efficacy, including Pharmacokinetics, of NNC 0129-0000-1003 when Administered for Treatment and Prophylaxis of Bleeding in Patients with Haemophilia A

Trial phase: 3

Applicable to: Denmark, Italy, Netherlands and Switzerland

Amendment originator:

This ~~confidential~~ document is the property of Novo Nordisk. ~~No unpublished information contained herein may be disclosed without prior written approval from Novo Nordisk. Access to this document must be restricted to relevant parties.~~

Table of Contents

	Page
1 Introduction including rationale for the protocol amendment.....	3
2 Changes to section 9 Trial supplies.....	3
9.1 Trial Product(s).....	3
9.4 Storage, Handling, Accountability and Destruction of Trial Product(s).....	3

1 Introduction including rationale for the protocol amendment

The rationale for this protocol amendment is the introduction of N8-GP in 3000 IU vials instead of 2000 U vials. The change is evaluated to be convenient for the patients since the use of N8-GP in 3000 IU vials will reduce the required injection volume compared to the use of N8-GP in 2000 U vials. In addition the number of N8-GP vials required for each injection will be reduced for some patients depending on the patient's bodyweight.

In this protocol amendment:

- Any new text is written *in italics*.
- Any text deleted from the protocol is written using ~~strike through~~.

2 Changes to section 9 Trial supplies

9.1 Trial Product(s)

The following trial products will be supplied by Novo Nordisk:

- ~~N8-GP 2000 U/vial 211 µg/vial as a sterile, freeze-dried powder in a 2-8 °C (36-46°F) stable formulation single use vial of 2000 U/vial to be reconstituted with 4.3 mL of 0.9% Sodium Chloride (NaCl) for i.v. injection.~~
- *N8-GP 3000 IU/vial as a sterile, freeze-dried powder in a 2-8 °C (36-46°F) stable formulation single use vial of 3000 IU/vial to be reconstituted with 4.3 mL of 0.9% Sodium Chloride (NaCl) for i.v. injection. The strength is given as IU, however, for N8-GP the strength IU equals U and these units can be used interchangeably.*

~~N8-GP 2000 U/vial 211 µg/vial powder must be reconstituted prior to administration. After reconstitution with 4.3 mL Sodium Chloride 0.9% solution each 2000 U vial contains 500 U/mL of N8-GP (4 mL can be withdrawn from the vial).~~ *N8-GP 3000 IU/vial powder must be reconstituted prior to administration. After reconstitution with 4.3 mL Sodium Chloride 0.9% solution each 3000 IU vial contains 750 IU/mL of N8-GP (4 mL can be withdrawn from the vial).* Sodium Chloride 0.9% will be provided by Novo Nordisk.

...

9.4 Storage, Handling, Accountability and Destruction of Trial Product(s)

~~N8-GP 2000 U/vial 211 µg/vial must be stored at 2-8 °C, protected from light.~~ *N8-GP 3000 IU/vials must be stored at 2-8 °C, protected from light*

Protocol Amendment no 21
Trial ID: NN7088-3859
UTN: U1111-1119-7416
EudraCT no: 2011-001142-15

~~CONFIDENTIAL~~

Date:
Version:
Status:
Page:

04 January 2018
1.0
Final
1 of 3

Novo Nordisk

Protocol Amendment

no 21

**to Protocol, version 12
dated 02 May 2016**

**(for Denmark, Italy, Netherlands and Switzerland:
Amendment to Protocol, version 13
dated 24 January 2017)**

Trial ID: NN7088-3859

pathfinder™ 2

**A Multi-national Trial Evaluating Safety and Efficacy, including Pharmacokinetics, of NNC
0129-0000-1003 when Administered for Treatment and Prophylaxis of Bleeding in Patients
with Haemophilia A**

**Trial phase: 3
Applicable to all countries**

Protocol Amendment no 21
Trial ID:NN7088-3859
UTN: U1111-1119-7416
EudraCT no: 2011-001142-15

~~CONFIDENTIAL~~

Date:	04 January 2018	Novo Nordisk
Version:	1.0	
Status:	Final	
Page:	2 of 3	

This confidential document is the property of Novo Nordisk. No unpublished information contained herein may be disclosed without prior written approval from Novo Nordisk. Access to this document must be restricted to relevant parties.

Table of Contents

1	Introduction including rationale for the protocol amendment.....	3
2	Changes	3

1 Introduction including rationale for the protocol amendment

The purpose of this amendment is to clarify when patients participating in pathfinder2 (NN7088-3859) can complete the trial.

From May 2018, patients will be offered to complete their visit schedule in NN7088-3859 and transfer to a new trial (NN7088-4410), where treatment with N8-GP can be continued. Transfer can take place when local authority approvals for the new trial have been obtained.

The planned LPLV date for NN7088-3859 remains unchanged.

In this protocol amendment:

- Any new text is written *in italics*.
- Any text deleted from the protocol is written using ~~strike through~~.

2 Changes

Section 7 Trial Schedule

.....

Planned date for FPFV: 01-Feb-2012

Planned date for LPLV: 03-Dec-2018*

**Patients may successfully complete the trial from May 2018, irrespective of their last scheduled visit.*

.....

PPX	Prophylaxis
PRO	Patient reported outcome
SAE	Serious adverse event
SAP	Statistical analysis plan
t_{1/2}	Terminal half life
V_{ss}	Volume of distribution at steady state
V_z	Apparent volume of distribution

1 Introduction

1.1 Trial information

This phase 3 trial is a multi-centre, multi-national, open-label, non-randomised trial evaluating safety, pharmacokinetics and clinical efficacy of NNC 0129-0000-1003 (hereafter referred to as N8-GP) when used for treatment of bleeding episodes and for long-term prophylaxis. The trial consists of a Main Phase followed by an Extension Phase part 1 and part 2. In the main phase, patients in the prophylaxis arm were receiving one single bolus dose of 50 U/kg body weight (BW) of N8-GP every 4 days (96 hours interval).

In the extension part 1, patients with a low bleeding rate on every 4 day prophylaxis in the main phase have the possibility of being randomised to either 50 U/kg BW every 4th day or to 75 U/kg BW once weekly dosing. If the patient for the last 6 months (180 days) prior to Visit 13/14 only had 0 - 2 bleeding episodes, the patient was eligible for randomisation. Patients who were not eligible to be in the randomised arm or patients who are eligible but unwilling to be randomised can stay on the same regimen as in the Main phase.

In the extension phase part 2, patients with a low bleeding rate (0-2 bleeding episodes during the last 6 months) on every 4 day prophylaxis have the possibility of changing to 75 U/kg BW once weekly dosing regimen. Patients who has been on 75 U/kg BW once weekly dosing during extension phase part 1 can continue on this regimen arm or change back to either 50 U/kg BW every 4th day if the patients want to. Patients on once weekly dosing who have more than 2 spontaneous bleeds within a 8 week period or are hospitalised due to a bleed need to change back to every 4 days regimen according to the protocol.

1.2 Scope of the statistical analysis plan

The scope of this SAP is to clarify the planed analysis for extension phase part 2 described in the protocol.

This SAP is based on the Protocol *A Multi-national Trial Evaluating Safety and Efficacy, including Pharmacokinetics, of NNC 0129-0000-1003 when Administered for Treatment and Prophylaxis of Bleeding in Patients with Haemophilia A* version 1.0 (30-Sep-2011) including Final Substantial Amendment no 1 version 1.0, NL (24-Oct-2011), Final Substantial Amendment no 2 version 1.0, Global (09-Dec-2011), Final Substantial Amendment no 5 version 1.0 FR (3-Feb-2012), Final Substantial Amendment no 6 version 1.0, Global (30-Mar-2012), Final Substantial Amendment no 8 RU (21-Jun-2012), Final Substantial Amendment no 10 version 2.0, Global (03-Dec-2012), Final Substantial Amendment no 11 version 1.0 IL (05-Dec-2012), Final Substantial Amendment no 12

Statistical Analysis Plan
Trial ID: 7088-3859-final
UTN: U1111-1119-7416
EudraCT No.: 2011-001142-15

~~CONFIDENTIAL~~

Date:	14 January 2019	Novo Nordisk
Version:	1.0	
Status:	Final	
Page:	5 of 25	

version 1.0, Global (05-Mar-2013), Final Substantial Amendment no 13 version 1.0, Global (03-May-2013), Final Substantial Amendment no 14 version 1.0, Global (12-Jul-2013), Final Substantial Amendment no 15 version 1.0, Global (28-Aug-2013), Final Substantial Amendment no 18 version 1.0, Global (29-Nov-2013), Final Substantial Amendment no 19 version 2.0, Global (29-Apr-2016), and the final version of the protocol for this trial (version 13, 24 January 2017).

2 Statistical considerations

The Pivotal part of the trial was reported based on all data from the Main Phase where all patients have reached at least 50 EDs (except for patients having had surgery as part of pathfinder™3), and all patients have had their first visit after 50 EDs where all planned assessments including inhibitors have been performed. All main conclusions from the trial are based on this reporting except for conclusions regarding every 7 day prophylaxis and long term safety/efficacy.

In the interim at end of extension phase part 1 all data from main phase up to the end of extension phase part 1 was analysed and reported. The main focus was on once weekly prophylaxis with every 4 day dosing as control where patients with low bleeding rate could be randomised to the two treatment arms.

The main reason for the interim for the ongoing extension phase part 2 including all data from the main phase and extension phase up to the cut-off is to collect additional safety and efficacy data.

2.1 Sample Size Calculation

The study has two co-primary endpoints for the Pivotal part that both need to succeed for the study to succeed. The co-primary endpoints can reasonably be considered approximately independent and combined power then becomes the product of the individual power for each co-primary endpoint. For further detail, see section 18.1 in the protocol.

2.2 Statistical Methods

2.2.1 General Considerations

Novo Nordisk A/S will be responsible for the statistical analysis. All tests will be performed as 1-sided tests on 2.5% significance level. All bleeding endpoints will be evaluated based on bleeding episodes requiring treatment with N8-GP. Non-treatment requiring bleeding episodes that coincide with regular prophylaxis doses are not included in the analyses.

Multiple bleeding locations occurring from the same event (e.g. due to a bicycle accident) or at the same time point will be counted as one bleeding episode and only one haemostatic response will be considered for the bleeding episode. In case different responses were registered for different bleeding locations in such a bleeding episode, the worst response will be used in the analysis. As stated in the protocol, a re-bleed is defined as a worsening of symptoms in the same location after an initial period of improvement, either on treatment or within 72 hours after stopping treatment. If a bleed occurs in the same location later than 72 hours after stopping the treatment it is

considered a new bleed. Re-bleeds will only be considered for joint bleeds since the specific location for other bleeds e.g. in subcutaneous are not captured in the database.

In the sub analyses of annualised bleeding rate where there are less than 5 patients in a sub-group, model based estimation will not be done. If no bleedings occur in a sub-group, then the confidence interval will not be calculated.

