5.3.2 Treatment of Bleeding episodes

A treatment requiring bleeding episode is in this trial defined as a bleed that require treatment with a coagulation factor product e.g. N8-GP. If a patient experiences a treatment requiring bleed it must be treated as soon as it is identified (refer to Section [8.2.1](#)). The Investigator must always be contacted in case of a severe bleed and the patient should visit the site within 24 hours.

Mild/moderate bleeding episodes can be treated at home without contacting the site. For definition of the severity of a bleed please refer to section [8.2.1.1](#).

For the treatment of bleeding episodes, doses will be based on World Federation of Haemophilia (WFH) guidelines¹ (see Section [8.2.1](#)). For treatment of a bleed all on demand and prophylaxis patients will be treated with doses between 20-75 U/kg BW (the recommended standard dose will be 50 U/kg). Due to individual patient's bleeding pattern during the trial, an adaptation in dosing regimen to 50 U/kg twice weekly will be permitted at the investigator's discretion. If the dosing regimen is changed to twice weekly, doses should be separated by at least 3 calendar days and no more than 4 calendar days.

The dose for treatment of bleeding episodes is aimed to achieve an expected post injection level of at least 0.50 U/mL of FVIII.

Any dose used for treatment of a known active bleed must be recorded as treatment of bleed and not as prophylaxis treatment. When the bleed has resolved, the patient can resume the prophylaxis treatment.

If a dose for treatment of a bleed is taken, the next prophylaxis dose should follow the original dosing scheme and not be altered by the additional treatment of bleed administration. If a bleed occurs on the same day as the planned prophylaxis, the dose must be registered for the bleed and not as prophylaxis.

Number of doses and frequency of dosing is decided by the Investigator in relation to the particular bleed. The maximum dose to be administered to a patient within 24 hours (hrs) is 200 U/kg BW. The dose is recommended to be divided and only considered under exceptional circumstance such as serious trauma or severe bleeding episodes.

If a haemostatic response cannot be achieved after 48 hours using adequate doses of N8-GP treatment when treating bleeding episodes, another FVIII product may be selected at the discretion of the Investigator. The use of other FVIII products will result in withdrawal of the patient.

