- FVIII genotype (if documentation is not available in the patient chart and as allowed per local law. In addition, the Investigator, patient or LAR has the right to refuse), see section [8.3.7.5](#)

All results necessary for evaluating the inclusion and exclusion criteria, from local and central laboratory analyses must be available before determining whether or not the patient can continue in the trial in accordance with inclusion and exclusion criteria.

Training and Reminders:

- An appointment for Visit 2a, 2-3 weeks after visit 1, should be made
- Patient should continue with current coagulation factor product until 72 hours prior to Visit 2a. If treated with coagulation factors within the last 72 hours the visit should be rescheduled
- Patients in the prophylaxis arm participating in the PK session should be reminded that Visit 2a will require 4 days wash-out and consist of 4 visits to the site during a period of 4 days

Patients will be assigned to on-demand treatment or the prophylaxis arm. The decision to enrol into either the on-demand arm or the prophylaxis arm lies with the patient and Investigator.

8.1.2 Visit Schedule for Patients on Prophylaxis not Undergoing PK Evaluation and for Patients on On-Demand treatment

Visit 2a should take place as soon as possible upon confirmation of eligibility and 2-3 weeks after the Screening visit (Visit 1).

At visit 2a the patients will have their first dose of N8-GP (50 U/kg) BW administered at the site. The second dose (50 U/kg BW) is given at visit 2b 4 days after visit 2a. If a bleeding occurs during this period the patient must come to the site for treatment with N8-GP.

The samples taken post-dose must not be taken from the same vein as previously used for administration of N8-GP.

Patients will be provided with an eDiary and will be carefully trained in the use of this eDiary including instruction in reporting details of bleeding episodes and prophylactic treatment including doses administered at visits.

At Visit 2a the following assessments will be performed and/or recorded in the eCRF

- Confirmation of inclusion and exclusion criteria, see section [6.2](#) and [6.3](#)
- Withdrawal criteria, see section [6.5](#)
- Concomitant medication, see section [11](#)
- Check date and time of last coagulation factor administration (see section [8.4.3](#))
- AEs: before and after dosing, see section [12.1](#)
- Body measurements (weight only), see section [8.4.2](#)

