8.2 Efficacy Assessments

8.2.1 Bleeding Episodes

During the entire trial period all treatment requiring bleeding episodes will be entered by the patient or caregiver in the patient’s eDiary. In case a patient is unable to enter a bleeding episode in the eDiary or hospitalised the Investigator will have to report it in the eCRF as an unscheduled visit, please refer to section [8.1.5](#).

If a patient experience a bleeding episode at home, treatment with N8-GP should be initiated irrespective of severity of the bleeding episode, please refer to section [5.3.2](#) for details. If the bleed is mild/moderate, the treatment responsibility is with the patient, patient’s caregiver(s) and/or Investigator. For severe bleeding episodes, the treatment responsibility is always with the Investigator and the patient should contact the site and come to an unscheduled visit. Treatment of severe bleeding episodes should be initiated as soon as possible by the patient or caregiver, before coming to the site. It is the responsibility of the Investigator to assess the severity of the bleeding episodes and to ensure that all data is recorded correctly in the patient’s eDiary.

Joint bleeds are either categorised as target joint or non-target joint bleeds. Target joints are defined as 3 or more bleeding episodes in the same joint within 6 months. When there has been no bleed in this same joint for 12 months, such a joint is no longer considered a target joint.

For bleeding episodes the following will be recorded in Patient's eDiary or eCRF:

- Prophylaxis or treatment of bleed
- Date and time of onset of bleed
- Location of the bleed
- Cause of bleed (spontaneous, traumatic, minor surgery)
- Haemostatic drug used for
- Pain relieving medication
- Dose(s) and Time(s) of administration
- Other therapy used (compression, ice or other)
- Stop of bleed (date and time)
- Categorisation of the bleeding episode (mild/moderate or severe), in the eCRF
- Clinical evaluation of the haemostatic response (excellent, good, moderate or none)
- Bleed related days away from work or school
- Bleed related days using mobility aids

A need for haemostatic rescue therapy with another FVIII product will be assessed by the Investigator via phone or during the site visit. Patients treated with FVIII products other than N8-GP must be withdrawn from the trial.

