5.3.2 Treatment of Bleeding Episodes

...

Any dose used for treatment of a known active bleed must be recorded as treatment of bleed and not as prophylaxis treatment. When the bleed has resolved (*e.g. pain reduction and no increase in swelling*), the patient can resume the prophylaxis treatment.

If a dose for treatment of a bleed is taken, the next prophylaxis dose should follow the original dosing scheme and not be altered by the additional treatment of bleed administration. If a bleed occurs on the same day as the planned prophylaxis, the dose must be registered for the bleed and not as prophylaxis.

If a bleeding episode occurs between visit 2a and 2b, the patient must contact the site and preferably come to the site for treatment with N8-GP. In case of a bleeding episode between visit 2a and 2b that requires immediate treatment or the Investigator judges it as necessary, the patient can treat the bleed at home with his previous FVIII product..

If a haemostatic response cannot be achieved after 48 hours using adequate doses of N8-GP treatment when treating bleeding episodes, another FVIII product may be selected at the discretion of the Investigator. The use of other FVIII products will result in withdrawal of the patient (*exception: current FVIII product is allowed until 72 hours before visit 2a and in case of home treatment of a bleeding episode that requires immediate treatment between visit 2a and 2b*).

An electronic diary (eDiary) will be kept to register all bleeding episodes and their treatment (*except treatment with the patients' current FVIII product between visit 2a and 2b in case of a bleeding episode that requires immediate treatment at home. In this case the information will be entered into the eCRF*). The Investigator must review the eDiary data and rate the bleeding episodes at every visit. *The review of the eDiary must be documented.*

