8.3.7 Central Laboratory Assessments

.....

All blood samples including genotyping blood sample will be destroyed after finalisation of the trial report. Blood samples of patients who are suspected of inhibitors or who have developed inhibitors will be stored at least until evaluation of the clinical trial data by the authorities in the patient's country.

8.3.7.4 Viral Assessments (HIV, Hepatitis B and C):

Viral assessments ~~should~~ *must* be performed if status is unknown *or if known* or the investigator consider there is an indication to test

8.3.7.5 FVIII genotype testing:

At visit 1, all patients/LARs will be asked about documentation of previous FVIII genotype tests. If not available or if it needs to be re-tested FVIII genotype testing will be offered at visit 3~~4~~. Investigator and patients/LARs have the right to refuse to provide patient's FVIII genotype documentation or to refuse genotyping.

8.4.3 eDiaries:

...

- Bleeding episodes

...

- *Date and time* for Sstop of bleed (*e.g. pain reduction with no increase in swelling*)(~~date and time~~)

Trial product administration performed at the site should also be entered in the eDiary by the patient, *except the first two doses of N8-GP administrated at visit 2a and 2b. These will be entered into the eCRF by the site. If the patient have used their previous FVIII product to treat a bleeding episode between visit 2a and 2b, this information will be entered in the eCRF.*

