For patients who were withdrawn in the Pivotal part the planned exposure time will be until the end of the pivotal part as described above. For patients who were withdrawn in the main part after the pivotal part ended, the maximum expected exposure time will be used, i.e. 100 weeks as this is the maximum duration for main phase. For patients withdrawn during extension phase part 1, the planned exposure is 24 weeks (duration of extension phase part 1) added to the actual exposure in main

For calculations only including the randomised period, the planned exposure time will be the time from visit 14 to visit 17, i.e. 24 weeks. Patients that change from Q7D to non-randomised part of Q4D will have their bleeds imputed using a planned exposure time of 24 weeks using the same approach as in the pivotal part of the trial even though they are not withdrawn from the study. This is to avoid bias for randomized Q7D caused by patients withdrawing due to high bleeding rate.

Calculations of ABR for extension phase part 2:

For patients withdrawn prior to extension phase part 2, planned exposure is calculated as explained above. For patients withdrawing during extension phase part 2, planned exposure in extension phase part 2 will be calculated using the overall cut-date (15Aug2017) as planned end date. The actual exposure time in main and extension phase part 1 is added to the planned exposure time in extension phase part 2, to get the overall planned exposure time for a withdrawn patient.

Planned exposure time is only relevant for the treatment regimen the patient is on, when being withdrawn. Time on other regimens and time in surgery trial is subtracted when calculating planned exposure time.

For patients who withdrew within 1 month, imputation will be conducted by assuming an annualised bleeding rate of 24 (bleeds per year) for the missing period. This also applies to change from Q7D to Q4D in the randomised part of extension phase part 1.

Estimates of the annualised bleeding rates for each regimen will be provided together with the 95% confidence intervals as described in the protocol.

Sensitivity analyses:

Analysis applying a different model

A sensitivity analysis based on a negative binomial regression model with number of bleeding episodes requiring treatment as the outcome variable, and adjusting for exposure time will be performed.

Analysis without imputation to planned trial duration

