Only treatment requiring bleeding episodes will be considered in the above evaluations of ABR. Incidence rate of FVIII-inhibitor and haemostatic effect of N8-GP when used for treatment of bleeding episodes will be evaluated based on accumulated data (Main Phase + Extension Phase part 1).

Adverse events, consumption of N8-GP, recovery and pre-dose levels will be summarised based on accumulated data (Main + Extension Phase part 1) by treatment regimen combining the every 4 day dosing regimens. In addition, separate summaries including data from part 1 only will be presented by treatment regimen for the randomised subset of patients to support the main objective of part 1 of the Extension Phase.

Other safety endpoints will be summarised based on accumulated data (Main Phase + Extension Phase part 1). Binding non-inhibitory antibodies will be listed.

PRO endpoints at end the Extension Phase part 1 will be evaluated and presented as described in section 18.9.

Data from part 2 of the Extension Phase

The main objective of extension phase part 2 is to collect long term safety and efficacy data.

ABR will be calculated as for the co-primary endpoint in the main phase, but based on the accumulated data, i.e. combined data from main phase, extension phase part 1 and extension phase part 2. Furthermore, sensitivity analyses are performed based on actual bleeding episodes and exposure times (i.e. without imputation for withdrawn patients).

Incidence rate of FVIII-inhibitor and haemostatic effect of N8-GP when used for treatment of bleeding episodes will be evaluated based on accumulated data.

Adverse events and consumption of N8-GP will be summarised based on accumulated data by treatment regimen.

Incremental recovery will be summarised by visit for extension phase part 2 and furthermore be presented graphically in the following ways:

- By N8-GP production process (extension phase part 2 data)
- According to Anti-PEG-antibody status (accumulated data)

For Anti-CHO HCP-antibodies, the number of negative/positive samples will be summarised by visit.

Other safety endpoints will be listed and/or plotted based on accumulated data.

-

PRO endpoints for extension phase part 2 will be summarised by time since first dose (since timing of visits depend on treatment regimen). Time grouping will span a year, i.e. grouping being “1 - <2 years”, “2 - <3 years”,.... The two prophylaxis regimens will be considered as a combined prophylaxis treatment regimen.

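### The ABR counting rule is tied to N8-GP treatment, which is narrower than the protocol's own bleed definition, so a bleed treated only with another FVIII product can drop out of the numerator

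*SAP*

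**What the plan says.** The analysis rule in SAP 2.2.1, also inserted in Protocol 18.2.1 by Amendment 13, is: "All bleeding endpoints will be evaluated based on bleeding episodes requiring treatment with N8-GP". The sentence after it sets aside bleeds that needed no treatment and merely coincided with a regular prophylaxis dose.

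Protocol 5.3.2 defines the event more widely: "A treatment requiring bleeding episode is in this trial defined as a bleed that require treatment with a coagulation factor product e.g. N8-GP". N8-GP is there only an example, and Amendment 2 keeps that sentence.

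Elsewhere the SAP names no product. Section 2.10 says "Only treatment requiring bleeding episodes will be considered in the above evaluations of ABR", and the sensitivity analysis in Section 2.2.2 is a "negative binomial regression model with number of bleeding episodes requiring treatment as the outcome variable".

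The protocol allows one use of another product on treatment. Under 5.3.2 as changed by Amendment 6, if a bleed between Visits 2a and 2b needs immediate treatment or the investigator judges it necessary, "the patient can treat the bleed at home with his previous FVIII product". Home treatment in that window is exempt from withdrawal. Section 8.4.3, as amended, sends the record to the eCRF: "If the patient have used their previous FVIII product to treat a bleeding episode between visit 2a and 2b, this information will be entered". Outside the permitted exceptions, Protocol 8.2.1 says "Patients treated with FVIII products other than N8-GP must be withdrawn from the trial"; Amendment 6 adds the Visit 2a to 2b exception to that sentence.

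For withdrawn patients, SAP 2.2.2 carries the observed bleeding rate forward to planned duration. Those who leave within one month get 24 bleeds per year for the missing period. No sentence says how a bleed treated only with another FVIII product is counted.

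**The concern.** A breakthrough bleed on N8-GP prophylaxis is a prophylaxis failure whichever product stops it. If the counting rule is programmed as written, a bleed treated only with another product is not an event, while nothing removes the patient's time from the offset. Every such omission lowers the ABR that is compared with 8.5.

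The carry-forward exists to prevent favourable bias when frequent bleeders leave early. If the bleed that ended participation is itself uncounted, an understated rate is projected over the missing period.

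**Working it through.** **1. The plan's own figure.** Inputs from Protocol 18.1 as changed by Amendment 6: effective ABR 7.0, over-dispersion (OD) 5, 120 patients, about 12 months each, success limit 8.5, one-sided 2.5%.

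Power = Φ[(8.5 − λ)/√(OD·λ/120) − 1.96].

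With λ = 7.0 the standard error is √(5 × 7.0/120) = 0.540, and Φ(1.5/0.540 − 1.96) = 79.3%. The plan states 79%. The other rows also reproduce:

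| ABR | OD | Computed | Stated |
|---|---|---|---|
| 6.8 | 5 | 89.1% | 89% |
| 6.5 | 5 | 97.0% | 97% |
| 7.0 | 4 | 87.4% | 87% |
| 7.0 | 6 | 71.8% | 72% |

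**2. The Visit 2a to 2b window.** Protocol 8.1.2 says the second dose "is given at visit 2b 4 days after visit 2a". Assume a constant rate, and assume that every bleed in the window is treated only with the previous product. The second assumption makes the result an upper bound.

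- Bleeds lost per patient: 4/365.25 × 7.0 = 0.077, which is 0.077/7.0 = 1.1% of the ABR.
- Power: if 7.0 is the rate under the narrow count, the full rate is 7.077. The standard error becomes 0.543, and counting these bleeds lowers power from 79.3% to 74.6%.
- Error: at a true all-product rate of 8.5, the loss is 4/365.25 × 8.5 = 0.093 and the counted rate is 8.407. Then Φ(0.093/0.592 − 1.96) = 3.6% instead of 2.5%.

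**3. A withdrawal-causing bleed after month 1.** The SAP's example is 3 bleeds in 2 months with 12 months planned: 3 × 12/2 = 18. Suppose a fourth bleed, treated only with another product, ended participation. Counted, the figure is 4 × 12/2 = 24. One omitted bleed therefore removes 6, or 6/120 = 0.05 from the ABR. Without imputation it removes 1/120 = 0.008.

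The documents give no number of such patients, so the counts below are assumptions (120 patients, 12 months planned, OD 5, one omitted bleed each):

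| Patients | Left at month 2: ABR shift | One-sided error | Left at month 6: ABR shift | One-sided error |
|---|---|---|---|---|
| 1 | 0.05 | 3.0% | 0.017 | 2.7% |
| 3 | 0.15 | 4.4% | 0.05 | 3.0% |
| 5 | 0.25 | 6.3% | 0.083 | 3.4% |

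**4. Where no scaling occurs.** A bleed treated between Visits 2a and 2b does not trigger withdrawal, so its omission is not scaled unless the patient later withdraws for another reason. A patient who leaves within one month gets 24 per year for the missing period whatever was observed.

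**The case against.** The best answer is that SAP 2.2.1 states no exclusion. It speaks of bleeds requiring N8-GP, and the sentence that follows suggests the aim was to separate treated from untreated bleeds. The product-neutral wording in SAP 2.2.2 and 2.10 fits that aim, and Protocol 8.2.1 expects N8-GP to be started for any bleed at home. This stands as a reading of intent. It makes the correction uncontroversial, but it does not tell a programmer what to do with a bleed that never received N8-GP.

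Several stronger inferences are tempting and are not supported:

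- *Rescue bleeds are lost.* The route the protocol describes to another product is failure of haemostasis after 48 hours of N8-GP (Protocol 5.3.2 and 6.5). Those bleeds were treated with N8-GP and stay counted. Protocol 8.2.1.1 mentions the local emergency room but does not say another product is used there.
- *The imputation multiplies every omission.* It does so only for withdrawals after month 1, as step 4 of the working shows.
- *Haemostatic response is biased too.* That endpoint is the effect of N8-GP when used to treat bleeds, so a bleed never treated with N8-GP belongs outside it. No improvement is already a failure, and so is a missing response.

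The sizes are also bounds and scenarios. Amendment 6 asks patients bleeding between Visits 2a and 2b to contact the site and preferably be treated there with N8-GP, so the true loss should be below the bound.

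**Conclusion.** The definitions are inconsistent, and the narrower one, taken literally, favours the product. The documented loss is at most about 0.08 bleeds per patient, or 1.1% of the ABR, assuming a constant rate and previous-product treatment of every bleed in the window. Omission of a withdrawal-causing bleed could cost more per patient, but its frequency is unknown and probably low.

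A reader might infer that the pivotal result is undermined. The documents do not support that: they give no count of affected bleeds, and SAP Section 2 says the pivotal part has already been reported. What remains open is the accumulated ABR in SAP 2.10, which still includes main-phase data. The no-imputation analysis kept for the end of trial (SAP Section 3) removes the scaling but not the omission.

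**What to change.** Reconcile SAP 2.2.1 and Protocol 18.2.1 with Protocol 5.3.2:

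- For the ABR, count every bleed requiring any coagulation factor product, from the first N8-GP dose to the end of the patient's prophylaxis observation time. This must be the same period as the offset. It must not run into the follow-up visits after the EOT visit for inhibitor withdrawals, which also collect bleeds.
- Include bleeds between Visits 2a and 2b from the eCRF, and any bleed that led to withdrawal, before imputation.
- Keep the N8-GP restriction for haemostatic response.
- Report the number of bleeds treated only with another product, by phase. For the pivotal test, which an SAP edit cannot change, that count is what a reader needs.

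The cost is about a sentence of SAP text and one tabulation. Visit 2a to 2b treatments are recorded in the eCRF, and the eDiary items in Protocol 8.4.3 include the FVIII product used. The ABR may become slightly less favourable.
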